7.5 Reporting urgent safety measures

If any urgent safety measures are taken the CI/Sponsor shall immediately and in any event no later than 3 days from the date the measures are taken, give written notice to the relevant REC of the measures taken and the circumstances giving rise to those measures.

8. STATISTICAL ANALYSES

8.1 Sample Size and power considerations

Summary of sample size calculations

Assuming PAD prevalence of 50%, with 255 with PAD and 255 without PAD, the study will have 90% power to estimate an assumed sensitivity (or specificity) to a precision of the half width of the 95% confidence interval of 8.2%. For a sensitivity (or specificity) of 80% this half width would increase to 10.2%. The level of significance was set at 1% to adjust for the 5 tests and ensure the overall level of significance does not exceed 5%. Power calculations used R.4.0.0 power.diagnostic.test in package MKmisc. The sample sizes for estimating likelihood ratios will also be estimated.

In the TrEAD study, PAD prevalence was 66%. As there will also be recruitment from primary care, with a lower PAD prevalence (34), the estimate to reflect the findings of our systematic review have been adjusted; prevalence of 50% across 18 studies (11). In TrEAD, TBPI could not be performed in 20% of patients. A similar proportion may be unable to tolerate exercise ABPI. It is estimated that 10% of patients may drop out prior to the reference test. Therefore, the sample size has been inflated by the cumulative missingness across all groups (30%) to be certain of having enough power for each and every test comparison. Thus, we aim to recruit a total of 730 patients.

During a study monitoring meeting in February 2023 with the funder, NIHR, it was agreed for the study sample size to be reduced from 730 to 584 based on the current attrition rate of 13% (as opposed to 30% estimated when the trial was designed). To account for those participants that may not get their reference test performed within the set time frame, a final recruitment target of 600 was agreed with the NIHR in August 2023.

Details of sample size calculations

We used R.4.0.0 routine power.diagnostic.test in package MKmisc to calculate 90% power at a notional 5% level of significance for both the sensitivity and specificity. If we assumed a 90% sensitivity (or specificity) we need 510 evaluable participants (which at 50% prevalence would be 255 with PAD, and 255 without PAD). This would allow the sensitivity (or specificity) to be calculated to within \pm 8.2% (the half-width of the 95% confidence interval). For a lower assumed sensitivity (or specificity) of 80% this would increase to \pm 10.2%. The estimated precision will also be calculated given these numbers for other diagnostic performance statistics such as the positive and negative predictive values, and the positive and negative likelihood ratios.

The sample size was re-calculated in February 2023 based on the current attrition rate of 13% (as opposed to 30% estimated when the trial was designed).

Sample size calculations for inter- and intra- rater reliability

In terms of sample size, an indicative calculation shows that using McNemar's paired test on correlated proportions, with 100 participants, with no loss to follow up, the study would have 90% power at a 5% level of significance to detect a difference of 0.17 in the discordant results (positive – negative vs. negative – positive) between two tests (e.g. 0.22 positive-negative vs. 0.05 negative-positive).

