8.4 Statistical Analysis

The five individual tests (and the sixth exploratory test in four sites) will be compared against the reference test (CTA/MRA), calculating standard diagnostic accuracy metrics of sensitivity, specificity, predictive values, likelihood ratio, and diagnostic odds ratio (using the bivariate model approach implemented in R). 95% confidence intervals calculated at 99% to adjust for the five comparisons will be presented. The robustness of the findings to any observed patterns of missing data will be assessed, which are expected to differ by test. A multiple imputation approach will be used assuming the data are missing at random. In addition, and probably more consistent with the likely missing data generating mechanisms, sensitivity type analyses assuming the data are missing not at random (i.e. informatively missing) will be explored. This would attempt to identify different types of missing data by an underlying reason or reasons, and then imputing values that capture plausible measurements for those missing data. The ?-adjustment approach given by van Buuren will be followed ([Flexible Imputation of Missing Data, Chapman and Hall, 2018, section 3.8ff](#)), and also the recommendations of Molenberghs & Kenward ([Missing Data in Clinical Studies, Wiley, 2007; Section 19ff on sensitivity analyses](#)). These approaches would allow the set of reasons for missing values to vary across the tests. The purpose is to stress the calculated findings to test their robustness to the observed patterns of missing data.

The subgroups of disease severity (both clinically and radiologically defined as detailed below) will be explored and those with/without neuropathy or DFU. The subgroups in the Statistical Analysis Plan will be pre-specified. Any further subgroup analysis (e.g. if suggested later by new data external to the study) will be labelled exploratory. Pre-specified subgroup analyses will be unlikely to be adequately powered. Clinical severity will be graded according to the severity of symptoms (from least to most severe; asymptomatic, intermittent claudication, rest pain and tissue loss). Severity will be measured radiologically using the ANGIO-score as outlined in section 5.7. Both will be analysed as pre-specified subgroup analyses in the Statistical Analysis Plan.

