4.5 Secondary analyses

4.5.1 ROC analysis

The following analyses will be obtained through the same ROC analysis performed in the primary outcome analysis for each diagnostic test:

- a) The specificity of each diagnostic test compared against the reference test. Specificity refers to the ability in correctly identifying participants who do not have PAD. Tests generating continuous outcomes (ABPI, TBPI and exercise ABPI) shall also be evaluated for performance based on optimised thresholds derived from Receiver Operating Characteristics (ROC) analysis. This will involve calculating, for a range of cut-points, the specificity of each continuous outcome diagnostic test with respect to the reference test for assessing PAD.

- b) The positive likelihood ratio (i.e. the ratio between the probability of a positive test result given the presence of PAD and the probability of a positive result given the absence of PAD; sensitivity/(1-specificity)) and the negative likelihood ratio (i.e. the ratio between the probability of a negative test result given the presence of PAD and the probability of a negative result given the absence of PAD, (1-sensitivity)/specificity) shall be calculated.
- c) The positive predicted value (i.e. the probability of the presence of PAD when the test is positive; a/(a+b)) and the negative predicted value (i.e. the probability of the absence of PAD when the test is negative; d/(c+d)) shall be presented.
- d) The diagnostic odds ratio is along with the associated 95% CI (calculated at 99% to adjust for the five or six comparisons) will be presented.
- e) Inter and intra-rater reliability shall also be assessed for each diagnostic test and for the reporting of the reference tests (as described in the Section 2)

4.5.2 *Combinations of tests*

The protocol says that an approach described by Pepe and Thompson [2] was to be used which examines linear combinations of the underlying tests was to be used. However, the paper specifies that this method is extremely complex when we wish to consider including more than two tests in the model. So that final models are comparable, a logistic regression approach shall be used instead.

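### Protocol 8.1 gives 8.2 and 10.2 points as 95% CI half-widths with 255 per group; the half-widths are about 3.7 and 4.9 (4.8 and 6.5 at 99%), and the sidedness behind the 90% power is not stated

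*Protocol*

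**What the plan says.** The summary in Protocol 8.1 assumes 50% prevalence, giving 255 participants in each disease group (510 evaluable). It claims 90% power to estimate a sensitivity or specificity "to a precision of the half width of the 95% confidence interval of 8.2" points and continues: "For a sensitivity (or specificity) of 80% this half width would increase to 10.2" points. The details part of 8.1 shows that the first figure belongs to an assumed value of 90%, and it repeats the label: "8.2% (the half-width of the 95% confidence interval".

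Two significance levels appear. The summary says "The level of significance was set at 1% to adjust for the 5 tests", in order to "ensure the overall level of significance does not exceed 5" per cent. The details say the routine was used "to calculate 90% power at a notional 5% level of significance for both the sensitivity and specificity". Neither says whether the test is one- or two-sided. Both name the R routine and package.

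For reporting, Protocol 8.4 plans "95% confidence intervals calculated at 99% to adjust for the five comparisons will be presented", and SAP section 2 reproduces that sentence. SAP 4.5.1 also has an interval "calculated at 99% to adjust for the five or six comparisons", but there it applies only to the diagnostic odds ratio.

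**The concern.** A 95% interval for a proportion near 90% with 255 observations is much narrower than plus or minus 8.2 points, so the stated sample size and the stated precision cannot both be right as labelled. Sensitivity is the primary endpoint, and these are the only precision figures given for it. The 510 evaluable participants behind them are also the base for the recruitment target.

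A second issue follows. If 8.2 and 10.2 are really margins from a hypothesis test, relabelling them is not enough. The 90% power statement is then true or false depending on sidedness, which the protocol does not give.

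**Working it through.** **Inputs (Protocol 8.1 and 8.4).** n = 255 per disease group; assumed sensitivity or specificity p = 0.90 or 0.80; stated half-widths 8.2 and 10.2 points; power 90%; alpha 1% per test, 5% overall; reporting level 99%.

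**Step 1. Can the plan's figures be reproduced as half-widths?** Wald half-width = z × √(p(1−p)/n).

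- p = 0.90, 95%: 1.960 × √(0.09/255) = 3.68 points
- p = 0.80, 95%: 1.960 × √(0.16/255) = 4.91 points
- p = 0.90, 99%: 2.576 × √(0.09/255) = 4.84 points
- p = 0.80, 99%: 2.576 × √(0.16/255) = 6.45 points

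Other interval readings, in points:

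| Reading at n = 255 | 90%, 95% CI | 80%, 95% CI | 90%, 99% CI | 80%, 99% CI |
|---|---|---|---|---|
| Wilson half-width | 3.67 | 4.89 | 4.84 | 6.42 |
| Clopper-Pearson half-width, at 230/255 and 204/255 | 3.84 | 5.09 | 4.99 | 6.61 |
| Clopper-Pearson half-width not exceeded with 90% probability | 4.25 | 5.35 | 5.52 | 6.95 |
| Wald full width | 7.36 | 9.82 | 9.68 | 12.9 |

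The third row reads 90% power as a 90% chance of achieving the width. No row gives 8.2 and 10.2.

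**Step 2. What sample size would give those half-widths?** n = z² × p(1−p)/h².

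- 95%: 1.960² × 0.09/0.082² = 51.4, so about 52; 1.960² × 0.16/0.102² = 59.1, so about 60
- 99%: 2.576² × 0.09/0.082² = 88.8, so about 89; 2.576² × 0.16/0.102² = about 102

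**Step 3. Where could 8.2 and 10.2 come from?** Treat them as margins: an exact binomial test of 0.90 − 0.082 = 0.818 against 0.90, and of 0.80 − 0.102 = 0.698 against 0.80. Reject when the number of correct results reaches the critical count c. The required n is the size from which power stays at or above 90%, because exact power moves up and down with n.

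| Test | n for 8.2 points | n for 10.2 points | Power at 255, 8.2 points | Power at 255, 10.2 points |
|---|---|---|---|---|
| One-sided 1% | 255 | 253 | 92.4% (c = 223) | 90.7% (c = 196) |
| Two-sided 1% | 290 | 282 | 85.1% (c = 225) | 87.9% (c = 197) |
| One-sided 5% | 175 | 170 | 97.8% (c = 220) | 98.1% (c = 191) |
| Two-sided 5% | 210 | 203 | 96.6% (c = 221) | 96.2% (c = 193) |

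The exact one-sided 1% test returns the plan's 255 for the 8.2-point margin. The normal approximation for that test gives 245.

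**Step 4. Smallest margin with at least 90% power at n = 255 (0.05-point grid).** One-sided 1%: 8.2 points at 90% and 9.9 at 80%. Two-sided 1%: 8.8 and 10.65 points. The reconstruction is therefore exact for 8.2 and close, but not exact, for 10.2.

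**The case against.** The strongest reply is that 8.2 and 10.2 are the difference parameter of the named routine and that only the wording slipped. On the one reading that returns 255, a one-sided 1% test, the 90% power statement is true. No document plans a two-sided test, and SAP 4.4 contains no test against a fixed value. The protocol names the software, so the sponsor can settle the matter by re-running it. The error also runs in the conservative direction, since the study will be more precise than stated.

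Much of this stands. The one-sided reading is the most likely origin, the two-sided power figures are conditional, and nothing here shows that the study is too small. The 99% wording in SAP 4.5.1 cannot support a 99% interval for sensitivity; that support comes from Protocol 8.4 and its copy in SAP section 2. The 5% in the details may simply mean the overall level that the summary divides among five tests, so it is unclear rather than shown to conflict.

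None of it rescues the label, because a test margin is not a confidence interval half-width. Nor does it remove the need to state sidedness: the planned 99% interval corresponds to a two-sided 1% test, and under that test the power claim fails for the stated margins.

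**Conclusion.** The concern holds. With 255 per group, 8.2 and 10.2 points are not 95% half-widths, nor 99% half-widths. The correct values are about 3.7 and 4.9 points at 95%, and 4.8 and 6.5 at 99%, so the stated figures are roughly twice the 95% values (8.2/3.68 = 2.2; 10.2/4.91 = 2.1). The choice of interval formula moves the correct values by less than 0.2 points.

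This conclusion needs only n and p from Protocol 8.1. The explanation of 8.2 and 10.2 as one-sided 1% margins is an inference: it fits 8.2 exactly and 10.2 approximately. If the intended test was two-sided at 1%, power is about 85% and 88% rather than 90%. The consequence is confined to the sample size justification, because no decision rule or analysis uses either figure.

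**What to change.** 1. State the precision correctly in both parts of Protocol 8.1, naming the method. For example: *With 255 participants per disease group, the expected half-width of the 99% confidence interval (Wald) is about 4.8 points at a sensitivity or specificity of 90% and 6.5 points at 80%; the 95% values are 3.7 and 4.9 points.*
2. Retrieve or repeat the original power run. If it confirms the reconstruction, describe 8.2 and 10.2 points as the margin between the assumed value and the lower value to be excluded, and give alpha and sidedness. With a one-sided 1% test, the 90% power statement stands. With a two-sided 1% test, either restate power as about 85% and 88%, or keep 90% and give the margins as about 8.8 and 10.65 points.
3. Make the significance level in the details agree with the summary: 1% per test, 5% overall, if that is what was meant.

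The cost is a text correction to Protocol 8.1 and a look at one software run. Enrolment and analysis stay as they are.

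### Protocol 8.1 gives two significance levels, 1% per test and a notional 5%, for one sample-size calculation; 255 per group fits 1% (apparently one-sided) and not 5%.

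*Protocol*

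**What the plan says.** Protocol 8.1 has a summary and a details subsection, both current text.

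- **Summary, level:** "The level of significance was set at 1% to adjust for the 5 tests", with the aim to "ensure the overall level of significance does not exceed 5" percent.
- **Summary, size:** "Assuming PAD prevalence of 50%, with 255 with PAD and 255 without PAD", 90% power, and a "precision of the half width of the 95% confidence interval of 8.2" points, rising to 10.2 points if the true value is 80%.
- **Details:** the same routine (power.diagnostic.test in MKmisc), used for "90% power at a notional 5% level of significance for both the sensitivity and specificity". Then: "If we assumed a 90% sensitivity (or specificity) we need 510 evaluable participants", split 255 and 255, with the same 8.2 and 10.2 points.
- **Analysis, Protocol 8.4:** "95% confidence intervals calculated at 99% to adjust for the five comparisons will be presented". SAP section 2 repeats this, and SAP 4.5.1(d) applies 99% to the diagnostic odds ratio.

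Neither part of 8.1 says whether the level is one- or two-sided. Neither document names the method for the 99% intervals.

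**The concern.** The two subsections share every other input and result, so they describe one calculation, and only one alpha can have been entered. The details subsection mentions neither the five tests nor a split of alpha. Its reliability calculation, a paragraph later, uses a 5% level as an ordinary alpha. A reader would therefore take 5% as the level behind 255.

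Sensitivity is the primary endpoint, and 510 evaluable participants is the base on which the recruitment target was set at 730, cut to 584 and then fixed at 600. Someone who checks that base at 5% would conclude that 350 to 420 evaluable participants were enough (2 × 175 to 2 × 210), and would misjudge the room left after the cut.

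The 8.2 and 10.2 points are also labelled half-widths of a 95% interval. That adds a third apparent level to the same sentence and does not fit the group size.

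**Working it through.** **Inputs (Protocol 8.1).** Power 90%; assumed value p1 = 0.90 with margin d = 0.082, or p1 = 0.80 with d = 0.102; n = 255 per disease group.

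**Assumption.** The routine tests one proportion against p0 = p1 − d, that is 0.818 or 0.698. Its code was not available.

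**Exact method.** For each n, the critical count c is the smallest with P(X ≥ c | p0) ≤ alpha, and power is P(X ≥ c | p1). Exact power rises in a saw-tooth as n grows, so two sizes are shown: where power first reaches 90%, and from where it stays there.

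| Alpha | 90% / 8.2: first – stays | 80% / 10.2: first – stays |
|---|---|---|
| one-sided 5% | 155 – **175** | 155 – **170** |
| two-sided 5% | 191 – **210** | 195 – **203** |
| one-sided 1% | 235 – **255** | 241 – **253** |
| two-sided 1% | 277 – **290** | 270 – **282** |

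The plan's 255 is reproduced at a one-sided 1%: exactly in the 90% case and within two in the 80% case. No 5% row reaches it under either rule. If the 8.2 is a rounded figure (8.15 to 8.25), the one-sided 1% size is 256 to 248, and the largest 5% size is 211.

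**Check by normal approximation.** n = [(z_alpha·√(p0(1−p0)) + z_power·√(p1(1−p1))) / d]². For the 90% case, √(0.818 × 0.182) = 0.3859 and √(0.9 × 0.1) = 0.3.

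- One-sided 1%: [(2.326 × 0.3859 + 1.282 × 0.3) / 0.082]² ≈ 244.5, so 245.
- One-sided 5%: [(1.645 × 0.3859 + 1.282 × 0.3) / 0.082]² ≈ 154.5, so 155.
- Two-sided 5%: 194. Two-sided 1%: 283.

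**In reverse, margin for 90% power at n = 255 (exact).** In the order of the table rows:

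- 90% case: 6.5, 7.3, 8.2 and 8.8 points.
- 80% case: 7.9, 8.8, 9.9 and 10.6 points.

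The 90% case again points to a one-sided 1%. In the 80% case the stated 10.2 lies between the two 1% rows, so sidedness is less sharply identified there. Both 5% rows are clearly excluded.

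**The half-width label.** A plain 95% half-width at n = 255 is 1.96 × √(0.9 × 0.1 / 255) = 3.7 points at 90%, and 1.96 × √(0.8 × 0.2 / 255) = 4.9 points at 80%. At 99% they are 4.8 and 6.5 points. So 8.2 and 10.2 are margins of a power calculation and not interval half-widths.

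**Relation to the 99% intervals.** Power is taken as the chance that the lower limit of a two-sided 99% interval exceeds p0, with n = 255.

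| Interval method | 90% case: count needed, power | 80% case: count needed, power |
|---|---|---|
| Wald | 223, 92.4% | 196, 90.7% |
| Wilson or exact | 225, 85.1% | 197, 87.9% |

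The Wald counts equal the critical counts of the exact one-sided 1% test, so that power agrees with the design. With Wilson or exact intervals, 90% power at 255 needs margins of about 8.8 points (90% case) and 10.6 to 10.7 points (80% case; 10.61 exact, 10.65 by normal approximation).

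**The case against.** The best defence is that the word notional signals the overall level. The summary gives both numbers and their relation, 1% for each of five tests within 5% overall, and the details sit under the same heading. On that reading nothing was miscalculated and the text is only loose shorthand. This may well be so. It does not rescue the sentence as written, which attaches 5% to the routine's power and never mentions a split.

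A second objection is that a one-sided 1% is back-calculated. The exact match depends on taking the size from which power stays at 90%; power first reaches 90% at 235, and the 80% case gives 253. That stands as a limit on what can be said about sidedness. It does not help the 5% reading, which stops at 210 (211 allowing for rounding).

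Three stronger inferences are tempting, and the documents do not support them.

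- *Neither stated level agrees with the 99% intervals.* The summary's 1%, with no side given, is nominally the level of a 99% interval and has the same five-test rationale. A mismatch appears only if the calculation was one-sided, and then it depends on the interval method.
- *The stated 90% power is lost at analysis.* It falls with Wilson or exact intervals but holds with Wald intervals. Wald intervals are not the preferred choice, but the documents do not exclude them.
- *Five-test error control fails, or borderline counts change the conclusion.* Neither document tests sensitivity against 81.8% or any other performance goal. Sensitivity is estimated, and Protocol 8.4 fixes the reporting level at 99%.

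**Conclusion.** The inconsistency is real and confined to Protocol 8.1. One calculation carries two significance levels, and 5% cannot be the alpha that gives 255 per group: it would need about 175 (one-sided) or 210 (two-sided), against 255 at a one-sided 1%. Whether the 5% is a slip or shorthand for the overall level cannot be settled from the documents.

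The conclusion assumes a one-sample binomial comparison of p1 with p1 − d. That sidedness was one-sided is an inference from the match and is not stated. The 95% half-width label on 8.2 and 10.2 is wrong on any reading, since those half-widths are about 3.7 and 4.9 points.

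The design power against the planned 99% intervals is undetermined until the method is named: about 85% to 92% in the 90% case and 88% to 91% in the 80% case. The planned size, the recruitment target and the reporting level are not shown to be wrong.

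**What to change.** 1. The statistician confirms from the calculation record which alpha and sidedness were entered.
2. Align the details subsection of Protocol 8.1 with its summary. If confirmed, a suitable wording is: 1% per test (5% overall across the five tests), one-sided. It should not be inserted as fact before that check.
3. In both subsections, describe 8.2 and 10.2 points as the margins detectable with 90% power, and drop the 95% interval half-width label.
4. Name the method for the 99% intervals and state how the design level relates to them. With two-sided Wilson or exact intervals, give power at 255 as about 85% (90% / 8.2 points) and 88% (80% / 10.2 points), or give margins of about 8.8 and 10.6 to 10.7 points at 90% power. With Wald intervals, power is about 92% and 91%.

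The cost is wording in Protocol 8.1 and a line in the SAP naming the interval method. The stated power or margin may become slightly less favourable. Enrolment and procedures do not change.

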The PAD-scan will be performed using a portable ultrasound system (Mindray M7; Shenzhen, China) with a linear 6-14Hz transducer. The anterior tibial and posterior tibial artery will first be visualised at the ankle, using B-mode imaging and colour Doppler, in transverse and then longitudinal planes. Arterial spectral waveforms will then be sampled from the centre of each vessel using a Doppler angle of <60°. Waveforms will be optimised for interpretation by adjusting sample volume, sample size, Doppler scale, Doppler gain and wall thump filter settings.

Repeating index tests

The first 100 volunteering patients will have tests repeated on the same day by the same operator and also by another, blinded, operator for the assessment of intra- and inter-rater reliability. Tests will be performed using the same descriptions outlined above. A minimum of 10 minutes rest must be provided to the patient prior to each batch of tests to avoid influence from previous tests carrying forward.

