Combinations of tests will be explored to see if using more than one test has incremental diagnostic value. The combinations of tests that were clinically felt to potentially offer an improvement over individual tests will be pre-specified in the SAP, and then, acknowledging the paired data, use the approach of Pepe and Thomson (*Biostatistics*, 2000; 1, 2; 123-140 'Combining diagnostic test results to increase accuracy'), which looks at linear combinations of the underlying tests. Post-hoc checks will be made if there were combinations that were not pre-specified that performed even better, as hypotheses for subsequent evaluation.

It is important to quantify the ability of each of the 5 index tests to measure consistently the same measurement of interest on the same leg of the same subject using the same test kit in the same location and the same environmental conditions, within a short period of time. This quantification of the intra-rater repeatability (or reproducibility) will be undertaken using the test-retest approach (35,36). The inter-rater reliability (the agreement between two or more clinicians measuring the same subject, again as under the conditions above) using appropriate methodology (35,36) will be quantified. For the inter- and intra-rater repeatability, we will aim for a sample size of 100 per pair of index tests.

These reliability studies will be performed at the start of the study and analysed as soon as the data are mature. If an index test has unacceptable intra-rater repeatability, or unacceptable inter-rater reliability, it could be dropped from further consideration, following discussions with the independent TSC. Unacceptable intra- and inter-rater reliability will be assessed in two ways— first, in an absolute sense, by looking at the kappa statistics and using the published guidance as to what an acceptable magnitude is (Fleiss, J.L. (1981). *Statistical methods for rates and proportions* (2nd ed.). New York: John Wiley) with a kappa of <0.4 considered unacceptable. This is not unanimity over interpreting the magnitude of kappa statistics, so our second approach will compare the kappa statistics across the tests, and label unacceptable any tests that are substantially worse than the other tests.

Inter- and intra-rater reliability will also be assessed for the reporting of reference tests using the methods outlined above. Reference tests will not be repeated due to feasibility and ethical considerations.

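### The 90% power and the aim of 100 pairs for the reliability sub-study make no allowance for tests that cannot be done; TBPI and exercise ABPI can expect about 80 to 87 pairs and about 82-88% power.

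*Protocol*

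**What the plan says.** Protocol 8.1, under the heading on inter- and intra-rater reliability, describes its basis thus: "an indicative calculation shows that using McNemar's paired test on correlated proportions". It claims "90% power at a 5% level of significance to detect a difference of 0.17" in the discordant results, with the example "e.g. 0.22 positive-negative vs. 0.05 negative-positive". The claim carries a condition on numbers and loss: "with 100 participants, with no loss to follow up, the study would have 90% power at a 5% level of significance".

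Protocol 5.7 fixes who is repeated: "The first 100 volunteering patients will have tests repeated on the same day by the same operator", and also by a second, blinded operator. Sections 2.4 and 5.3 give the same limit of 100. Protocol 8.4, reproduced in SAP section 2, sets the target: "we will aim for a sample size of 100 per pair of index tests".

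Earlier in 8.1, the main sample size discussion says: "In TrEAD, TBPI could not be performed in 20% of patients. A similar proportion may be unable to tolerate exercise ABPI". Protocol 5.7 also accepts that exercise ABPI may be omitted or stopped early. The main sample was inflated at the design stage by 30% cumulative missingness. In February 2023 that allowance was replaced by an observed attrition of 13%. Neither allowance was applied to the reliability sample.

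**The concern.** The power statement and the target both equate 100 volunteers with 100 usable pairs for every index test. By the protocol's own expectation this will not hold for two of the five. The condition about loss to follow-up does not cover the gap: the repeats are done on the same day, so the likely loss is a test that cannot be performed, not a patient who fails to return.

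The reliability results have a use. Protocol 8.4 allows a test to be dropped after discussion with the TSC if its kappa is below 0.4 or substantially worse than that of the other tests. TBPI and exercise ABPI would enter that comparison with fewer pairs than the plan states, and readers of 8.1 would credit them with more power than the design gives.

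**Working it through.** **Inputs from protocol 8.1.** Discordant proportions p10 = 0.22 and p01 = 0.05, so d = 0.17 and ψ = p10 + p01 = 0.27. Significance level 5%. TBPI failure 20%; exercise ABPI possibly similar. Observed attrition 13%. The 10% allowance for dropout before the reference scan does not apply, because same-day repeats do not need the scan.

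**Assumption.** Two-sided test. The protocol does not say, but a one-sided normal approximation gives 95.7% at 100 pairs and does not reproduce the stated figure.

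**Formula (normal approximation).** Power = Φ[(d√n − 1.96√ψ) / √(ψ − d²)], with √ψ = 0.5196 and √(ψ − d²) = √(0.27 − 0.0289) = 0.4910. The exact figures come from full enumeration of the exact McNemar test.

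**Step 1: the plan's own figure.** n = 100: (1.700 − 1.018)/0.4910 = 1.388, so power is 91.7%. The exact test gives 90.4%. The stated 90% reproduces.

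**Step 2: pairs needed for 90%.** n = (1.96 × 0.5196 + 1.2816 × 0.4910)² / 0.17² = 93.9, so 94 pairs by the normal formula. The 100 therefore carries about 6% slack on that formula, and almost none by the exact test.

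**Step 3: expected pairs for TBPI and exercise ABPI.**

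| Failure rate | Pairs | Normal approximation | Exact |
|---|---|---|---|
| 0% | 100 | 91.7% | 90.4% |
| 13% | 87 | 87.6% | 85.5% |
| 20% | 80 | 84.7% | 82.1% |

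For 80 pairs: (0.17 × 8.944 − 1.018)/0.4910 = 1.023. For 87 pairs: (0.17 × 9.327 − 1.018)/0.4910 = 1.155.

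**Step 4: why 13% can serve as an upper bound.** 510/0.70 = 729 and 510/0.87 = 586, close to the planned 730 and the revised 584. The 13% therefore stands in for the whole 30%, which combined test failure and dropout. If it covers the same losses, test failure alone is at most 13%. The documents do not split it.

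**Step 5: detectable difference.** At 80 pairs, with p01 held at 0.05, 90% power needs p10 of about 0.240 (normal) or just under 0.25 (exact). That is a difference of about 0.19 to 0.20 instead of 0.17.

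**Step 6: effect on kappa.** With 50% positivity assumed, chance agreement is 0.5 and SE ≈ √[po(1 − po)/n]/0.5, where po = 0.5 + 0.5κ. At κ = 0.4 (po = 0.7) the 95% half-width is 0.18 with 100 pairs and 0.20 with 80. At κ = 0.6 (po = 0.8) it is 0.16 and 0.18.

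**The case against.** The strongest reply is that nothing is miscalculated. The figure is labelled indicative, its no-loss condition is stated, and 8.4 only aims for 100. All of that stands: a reader might infer an arithmetic error, and there is none. What remains is that the protocol itself expects the condition to fail for two tests and does not say what follows.

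A second reply is that 20% is a design-stage figure from another study, only tentative for exercise ABPI, and since overtaken by 13%. Volunteers for repeat testing may also be fitter than the average participant. This stands as a reason to give a range. At about 6% failure or less, normal-approximation power would stay at 90%. But at 13% power is still under 90% by both methods, and no document gives a failure rate for the volunteers.

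A third is that the drop rule uses kappa, not McNemar, follows TSC discussion, and would seldom turn on a half-width change of about 0.02. That is fair, and it limits the consequence. The target of 100 per pair is missed whichever statistic is used.

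A fourth is that SAP 3.3 already requires the number analysed to be reported for the analyses in 4.5, which include reliability, and that protocol 5.6 and 5.7 record tests not performed. Also true. Neither asks for a confidence interval on kappa, or for the pair count to be set beside it before a drop decision.

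Two further inferences are not supported. SAP 3.4 treats a negative result in one vessel with the other missing as inconclusive, and a reader might conclude that this costs TBPI more pairs. It cannot, because TBPI is excepted from the two-vessel rule. A reader might also suppose that many patients who manage the exercise once will not repeat it, taking pairs well below 80; the documents give no rate for that.

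**Conclusion.** The stated power and the aim of 100 pairs are not delivered for TBPI and exercise ABPI on the protocol's own expectations. Expected pairs are about 80 at 20% failure and about 87 if 13% bounds it. Power is then about 82-88%, a loss of roughly 4 to 8 points against the same method at 100 pairs. For tests completed twice in nearly all 100 volunteers, about 90% holds; the documents give no failure rate for the Doppler tests or resting ABPI.

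This rests on a two-sided test, the protocol's single discordance scenario, and the transfer of whole-sample failure rates to the volunteers. The defect is a missing allowance in a planning statement. It does not show that the sub-study is inadequate or that a drop decision would change.

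**What to change.** - **Protocol 8.1:** say that about 90% power applies only to tests completed twice in nearly all 100 volunteers. For TBPI and exercise ABPI give a range of about 82-88% (80 to 87 pairs), with the failure rates assumed and the sidedness of the test.
- **Protocol 8.4 and SAP section 2:** replace the aim of 100 per pair with 100 volunteers and the expected evaluable pairs for each test.
- **SAP 4.5.1(e):** report each kappa with its achieved number of pairs and a confidence interval, and have these available before any decision to drop a test.

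The cost is wording in two documents and a slightly less favourable stated power for two tests. Keeping 100 pairs at 20% failure would take 100/0.80 = 125 volunteers, but that is not needed to correct the statement, and no extra enrolment is proposed.
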